**Experimental:**

Randomized controlled clinical trial (RCT) - this is the “gold standard” for clinical research. These prospective studies have at least two groups. Patients meeting strict inclusion/exclusion criteria are enrolled and randomly assigned to receive either an experimental intervention or to receive what is considered to be an acceptable alternative – usually the current standard of care or a placebo (e.g., study of hyaluronic acid injection versus cortisone for arthritis).

Other – please describe:

**2. Who will be recruited and enrolled? – answer each question individually**

*Inclusion Criteria: list characteristics that potential subjects and controls need to have and rationale for any special classes of subjects (minors, mentally disabled, pregnant women, employees, prisoners). Use a bullet format, if applicable.*

Patients will be recruited from the practice of the study surgeon ([name]). Inclusion criteria will include the following:

- Age  $\geq$  12 years old - <45 years old
- Scheduled for elective periacetabular osteotomy

Formatted: Underline

*Exclusion Criteria: list characteristics that would cause you to exclude potential subjects and controls and rationale for exclusion of any special classes of subjects (minors, mentally disabled, pregnant women, employees, prisoners). Use a bullet format, if applicable.*

All patients will be asked to discontinue acetylsalicylic acid (ASA), antiplatelet agents, and hormone replacement and hormonal contraceptive agents at least 7 days prior to surgery. Other than ASA, these agents will be held 6 weeks postoperatively.

- Preoperative use of an anticoagulant (Plavix, warfarin, lovenox, etc.)
- History of hypersensitivity to tranexamic acid
- History of thromboembolic event (e.g., PE or DVT)
- History of subarachnoid hemorrhage
- History or evidence of hepatic dysfunction (AST/ALT>60) or renal dysfunction (Cr>1.5 or GFR<30)
- Coronary stents or prior diagnosis of coronary artery disease
- Color blindness
- Leukemia
- Congenital or acquired coagulopathy as evidence by INR >1.4 or PTT > 1.4 times normal, or Platelets <150,000/mm^3 on preoperative laboratory testing
- Use of hormone replacement therapy or hormonal contraceptive agent within 7 days prior to surgery
- Pregnant
- Breastfeeding
- Donated preoperative autologous blood
- Younger than 12-years-old and older than 45
- Preoperative hemoglobin < 10 g/dL
- Concomitant open procedures (e.g., femoral osteotomy or osteochondral allograft)

a) *Describe how you will identify and recruit potential subjects for participation in the study.*

This trial will be registered on ClinicalTrials.gov. This All patients undergoing PAO by the study surgeon ([name]) will be identified in his office and screened for eligibility as potential patients for participation in the study. A research assistant will review the office and operative calendars of the study surgeon each week to identify and recruit potential patients. The assistant will record on the CONSORT diagram any reasons for ineligibility/exclusion.

b) *Who will obtain consent? When and where will consent be obtained? List the names and roles of all individuals who are designated to obtain consent.*

The surgeon, a co-investigator or research assistant will obtain consent prior to surgery, at the patient's preadmission screening visit. All authors on the protocol, in addition to their research assistants, will be designated to obtain consent.

c) *How many subjects will be enrolled? If controls are being used, state how they will be identified and consented.*

Wingerter, et al.[11] demonstrated that IV TXA may reduced post-PAO total blood loss by 314.4 mL (30.8%). A retrospective chart review of all PAOs performed by the PI at HSS found a mean  $\pm$  SD calculated blood loss of 1295.98 mL  $\pm$  383.27 mL. Studies in the total hip literature have defined 250 mL as a clinically important difference in blood loss [18]. Therefore, we will power the study to detect a 250 cc difference calculated total blood loss between groups. Our analysis shows that 40 patients are required in each arm of the study (80 patients total) to achieve 82% power with an independent-sample t-test and statistical significance set to alpha equal to 0.05.

d) *What age range will be used?*

Patients  $\geq$  12 years old will be screened for study eligibility.

**3. Interventions or Observations – what data are going to be collected and from what source? Be specific and describe the interventions or observations in detail. Answer each question individually**

*a) What are the procedures, treatments, and/or interventions, as well as sources of research material to be utilized, that will be part of this research project?*

PAO will be performed as per the surgeon's routine practice. In general, the operative extremity and hemipelvis will be prepped and draped in the usual sterile fashion. Prior to incision, the anesthesiologist, who will be blinded to the study group, will administer either 10 mg/kg, up to a maximum of 1 g, of IV TXA (diluted in 50 mL of normal saline, with a maximum concentration of 100 mg/mL) or 50 mL of normal saline prepared by the pharmacy. Only anesthesiologists agreeing to participate in the study will be paired with the study surgeons. A Smith-Petersen approach will be used, and standard surgical techniques for intraoperative hemostasis will be utilized. Intraoperatively, a cell saver will be used, and the volume (mL) of autotransfusion will be recorded. The ischial, pubic, supra-acetabular, and retro-acetabular osteotomies will be performed, and the surgeon will then re-orient the acetabular fragment to achieve the desired correction. Cortical screws will then be placed for definitive fixation. After all hardware is placed, the wound will be thoroughly irrigated and suctioned. The anesthesiologist will administer either a second dose of IV TXA as described above or a 50 mL bolus of normal saline, as prepared by the pharmacy, and the wound will be closed in layers. Routine, daily inpatient CBC data will be reviewed. Inpatient and office records will be accessed to help identify postoperative complications.

*b) Indicate what data will be collected, who will collect it, when it will be collected, and from what source – medical records, private office charts, registries, radiographic sources and/or patient.*

Surgeons, orthopedic surgery residents, physician assistants and research assistants involved in the study will assist in data collection. Sample data collection sheets are attached.

For each patient, we will collect demographic data, preoperative CBC data, intraoperative cell saver autotransfusion volumes, postoperative number of units transfused, and postoperative CBC data. This information will be gathered from the perioperative medical records and electronic medical records. Standard preoperative radiographs will be reviewed to assess the severity of each patient's preoperative hip deformity.

In regards to identification of study patients, a sticker will be placed on the front of each patient's chart identifying them as a study patient, and their enrollment will be communicated in the clinician rounding notes for each patient.

Calculated total blood loss will be determined [19-21].

**Data recorded from the electronic medical record will include:**

- Date of surgery
- Patient age at the time of surgery
- Patient gender
- Patient height (cm) and weight (kg) at time of admission

- Transfusion requirement during inpatient stay (units required)
- Postoperative day and time of discharge
- Preoperative CBC data and coagulation study data
- Postoperative hemoglobin on all inpatient days postoperatively (g/dL)
- Chart review of progress notes for evidence of clinically significant VTE
- Chart review of progress notes for evidence of reoperation, hematoma, seroma, or postoperative infection

**Data recorded from the operating room record will include:**

- Anesthetic used (e.g., regional, general, etc.)
- Operative times (minutes)
- Intraoperative transfusion requirements (units of blood)
- Use of cell saver intraoperatively (autotransfusion volume, mL)

**Data recorded from review of the radiological studies:**

- Preoperative center-edge angle (CEA), Tönnis angle, lateral CEA, and acetabular version
- Postoperative documentation of VTE (e.g., ultrasound confirming DVT, or CT confirming PE)
- Postoperative documentation of hematoma or seroma

**Data recorded from outpatient postoperative office records will include:**

- Chart review of progress notes for evidence of clinically significant VTE
- Chart review of progress notes for evidence of reoperation, hematoma, seroma, or postoperative infection
- Chart review of progress notes for documentation of reoperation

c) *If controls are included in this proposal, please include the following: describe how they will be matched with the study subjects; state whether the controls will have identical data recorded, or describe any differences compared to the intervention subjects.*

Patients will be randomized to either the intervention or control group, as per randomization protocol described elsewhere in the proposal. For patients who are randomized to the control group, study data will be collected in the same manner as for the intervention group.

e) *Are all the tests or images part of standard of care? If not, identify which tests are not standard of care. What source of funds will be used to pay for them?*

All tests and imaging are considered standard of care.

e) *Create a data collection sheet and include all data/datafields to be collected. Include time points of data collection and final outcome time point. Attach the data collection sheet.*

Please see attached.

f) *Attach/upload all questionnaire(s) to be used. Provide information about the validity, reliability and appropriateness of the instrument(s) for your study.*

g) If randomization is involved, state how the randomization will be done, by whom, when, who will ensure randomization is carried out, and whether anyone will be blinded to the randomization group. Clearly explain the treatment arms of the study.

*Randomization Process:*

The patients will be randomized into one of 2 groups: (1) 10 mg/kg, up to a maximum of 1 g, of IV TXA (diluted in 50 mL of normal saline, with a maximum concentration of 100 mg/mL) or (2) 50 mL of normal saline prepared by the pharmacy. Assignment of patients will be made prior to the initiation of enrollment for the study. Patients will be randomized using a computer generated (SAS PROC) block randomization schedule to ensure equivalent numbers of patients in each group over the course of the study in case early stopping is required. Randomization will be stratified by sex and surgery type (PAO or Scope/PAO) so that the number of male patients and Scope/PAO patients will be balanced in each study group between trial arms.

The randomization schedule will be generated by the HSS Epidemiology & Biostatistics Core with the randomization list provided to the investigators prior to initiation of patient recruitment. It will be a double-blind experiment with all parties, except the pharmacy, being blinded to the randomization schedule (surgeon, anesthesiologist, research assistant, and patient). Patient recruitment will continue until a total of 80 patients are enrolled.

*Treatment Arms:*

PAO will be performed as per the study surgeon's routine practice. In general, the operative extremity and hemipelvis will be prepped and draped in the usual sterile fashion. Prior to incision, the anesthesiologist, who will be blinded to the study group, will administer either 10 mg/kg, up to a maximum of 1 g, of IV TXA (diluted in 50 mL of normal saline, with a maximum concentration of 100 mg/mL) or 50 mL of normal saline prepared by the pharmacy. Only anesthesiologists agreeing to participate in the study will be paired with the study surgeons. A Smith-Petersen approach will be used, and standard surgical techniques for intraoperative hemostasis will be utilized.

Intraoperatively, a cell saver will be used, and the volume (mL) of autotransfusion will be recorded. The ischial, pubic, supra-acetabular, and retro-acetabular osteotomies will be performed, and the surgeon will then re-orient the acetabular fragment to achieve the desired correction. Cortical screws will then be placed for definitive fixation. After all hardware is placed, the wound will be thoroughly irrigated and suctioned. The anesthesiologist will administer either a second dose IV TXA as described above or a 50 mL bolus of normal saline, as prepared by the pharmacy, and the wound will be closed in layers. Routine, daily inpatient CBC data will be reviewed. Inpatient and office records will be accessed to help identify postoperative complications.

*Outcome Measures*

Primary outcome: Calculated total blood loss.

Secondary outcomes of interest: Postoperative allogeneic blood transfusion, and intraoperative cell saver utilization.

Calculated total blood loss will be determined from the difference between the preoperative hemoglobin and the lowest postoperative hemoglobin during the hospital stay (or the lowest postoperative hemoglobin prior to transfusion). Based on hemoglobin balance, the estimated blood loss will be calculated according to the formula by Nadler et al. [19]:

Hospital for Special Surgery

IRB# \_\_\_\_\_

Form 1 -Clinical Research Proposal Form

$$\text{Estimated Blood Volume (EBV)} = (k_1 \times \text{Height}^3 \text{ (m)}) + (k_2 \times \text{Weight (kg)}) + k_3$$

For men,  $k_1 = 0.3669$ ,  $k_2 = 0.03219$ , and  $k_3 = 0.6041$

For women,  $k_1 = 0.3561$ ,  $k_2 = 0.03308$ , and  $k_3 = 0.1833$

Multiplying the EBV by the hematocrit (Hct) gives the red blood cell (RBC) volume. As such, a change in the RBC volume can be calculated from a change in the Hct level [20, 21]:

$$\text{Total RBC volume loss} = \text{EBV} \times (\text{Hct Preop} - \text{Hct Postop})$$

Transfusions (mean volume per unit, mL) can be taken into account by calculating the total blood loss:

$$\text{Total blood loss (L)} = \text{Total RBC volume loss} + (\text{No. of Units Transfused} \times 0.285) / (\text{Hct Preop} - \text{Hct Postop}) / 2$$

The rate of perioperative blood transfusions, both intraoperative and postoperative, will be documented for analysis.

The criteria for transfusion of blood products will be a hemoglobin level of  $< 8.0$  g/dL or a hemoglobin level of  $< 10.0$  g/dL with clinical signs of symptomatic anemia (e.g., chest pain that was deemed to be cardiac in origin, congestive heart failure, unexplained tachycardia, or hypotension unresponsive to fluid replacement). Blood will be administered 1 unit at a time, and the presence of symptoms or signs will be reassessed. Of note, the chart of the patient will clearly indicate him/her as a study patient.

VTE prophylaxis will be standardized, with each patient receiving 3 weeks of prophylaxis with 325 mg of oral aspirin twice daily. All patients will also receive a comprehensive, multidisciplinary approach to postoperative care with mechanical (sequential compressive device) prophylaxis in-house, early mobilization with physical therapy, medical optimization, and regional anesthesia, if appropriate.

**4. What is the long-term significance? - state the potential long-term benefits of the study, why it is important and its potential significance.**

The risk of excessive blood loss and blood transfusion in young, healthy patients after elective surgery is an event that can be reduced with blood conservation protocols, which can include pharmacological agents like TXA. If the use of IV TXA in the PAO patient population significantly reduces total perioperative blood loss, then it would provide an efficacious and inexpensive method for reducing postoperative morbidity after PAO.

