**A. SPECIFIC AIMS OR RESEARCH QUESTIONS - answer each question individually.**

*1. What is the condition or intervention to be studied?*

Periacetabular osteotomy (PAO) is an elective reorientation surgery for the hip joint, typically for the treatment of hip dysplasia in young, otherwise healthy patients, which requires multiple pelvic osteotomies around the acetabulum [1]; a major source of its perioperative morbidity is blood loss [2]. The principal cause of postoperative blood loss after PAO is surgical trauma, with secondary activation of both the coagulation cascade and local fibrinolysis [3]. Tranexamic acid (TXA) is a synthetic derivative of the amino acid lysine that acts as competitive inhibitor of plasminogen activation, interfering with fibrinolysis [4]. Multiple studies and meta-analyses have shown that intravenous (IV) of TXA reduces postoperative bleeding and the need for transfusion after orthopedic surgery, including total joint arthroplasty, with no demonstrable change in the risk for postoperative complications, including venous thromboembolic events (VTE) [5-10]. However, there is no prospective data regarding TXA use for PAO, and, in our experience, PAO surgeons question and argue the use and disuse of TXA for this procedure.

In the PAO literature, allogeneic transfusion rates are as high as 58% [11], and blood loss can range to nearly 4 L [2, 11-17]. If autologous blood and intraoperative cell saver are considered along with allogeneic transfusions, the risk of perioperative transfusion can be as high as 94% [2].

Retrospectively, we reviewed 93 PAO cases performed by the principle investigator of this study. The average calculated blood loss was  $1.30 \pm 0.38$  L (range, 0.32 L – 2.65 L), and 33.3% of patients required at least one transfusion of allogeneic blood postoperatively. There has been one retrospective study examining the effect of IV TXA on blood loss and transfusion after PAO that showed that IV TXA may reduce total blood loss by 30.8% ( $p=0.001$ ) and transfusion rate by 58.6% ( $p=0.013$ )[11].

The goal of this randomized controlled, double-blinded trial is to assess the efficacy of IV TXA in reducing calculated total blood loss in patients undergoing PAO. Our specific objectives included analysis of (1) calculated total blood loss (primary outcome), (2) intraoperative cell saver utilization (secondary outcome), and (3) postoperative allogeneic blood transfusion (secondary outcome).

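### Section C.3(g) sends the randomization list to the investigators before recruitment, yet blinds everyone except the pharmacy to the schedule

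*Combined protocol and SAP*

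**What the plan says.** Two adjacent sentences in section C.3(g), Randomization Process, deal with access to the allocation sequence. The first has the institution's Epidemiology & Biostatistics Core generate the schedule, "with the randomization list provided to the investigators prior to initiation of patient recruitment". The second calls the trial double-blind, with "all parties, except the pharmacy, being blinded to the randomization schedule (surgeon, anesthesiologist, research assistant, and patient").

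Other places bear on who these people are and when the sequence exists:

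- Section C.3(g), just before: "Assignment of patients will be made prior to the initiation of enrollment for the study". The schedule is blocked and stratified by sex and surgery type.
- Section C.2(b), on consent: "The surgeon, a co-investigator or research assistant will obtain consent prior to surgery". The same answer then designates all protocol authors and their research assistants for this task.
- Section C.2, on recruitment: "Patients will be recruited from the practice of the study surgeon".
- Section A.1: "Retrospectively, we reviewed 93 PAO cases performed by the principle investigator of this study".
- Section A.1 also states the design: "The goal of this randomized controlled, double-blinded trial". Section C.3(a) and the Treatment Arms text of C.3(g) repeat the intent for one role: "the anesthesiologist, who will be blinded to the study group". The pharmacy prepares the infusions.

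**The concern.** The delivery clause names the investigators as recipients. The blinding sentence allows one exception, the pharmacy. The second sentence blinds people to the schedule itself, and not merely to an individual patient's group, so the two sentences appear to govern the same object and give opposite instructions about it.

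Two safeguards are at stake. The first is allocation concealment: someone who can see the next assignment can, knowingly or not, let it influence whom to approach, when to enroll and how to present the study. The second is blinding during care. Transfusion in the intermediate hemoglobin range depends on judged clinical signs (Outcome Measures in C.3(g)). Units transfused are a secondary outcome and also enter the formula for the primary outcome, calculated total blood loss. Knowledge of the arm could therefore reach the primary endpoint through a clinical judgement. The plan describes the trial as double-blinded and says in section B that it is meant to supply Level I evidence, and both claims depend on these safeguards.

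**Working it through.** No figure in the plan bears on this point, so the check is a comparison of texts.

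**Step 1: who receives the list, and when.** The investigators, before recruitment begins (C.3(g)).

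**Step 2: who must not see the schedule.** Everyone but the pharmacy. Four roles are named: surgeon, anesthesiologist, research assistant and patient (C.3(g)).

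**Step 3: do the two groups overlap?** The documents contain no definition of the investigators, so membership has to be inferred.

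- Section A.1 reports a series of these operations performed by the principal investigator, and section C.2(c) draws its standard deviation from the principal investigator's own cases. The principal investigator is therefore an operating surgeon.
- Patients come from the study surgeon's practice (C.2). That the study surgeon is among the investigators is very likely, though not stated outright.
- Section C.2(b) designates all protocol authors to obtain consent. Any investigator who is an author and holds the list is therefore also someone who may enroll patients.
- No text describes the pharmacy as an investigator, and the blinding sentence sets it apart from the other parties.

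On the natural reading, the groups overlap.

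**Step 4: would the list reveal future assignments?** Assignments are fixed before enrollment opens (C.3(g)), so a list with arm labels would show allocations still to come. The documents do not say whether the list carries arm labels. Nor do they say that it is coded, masked or sealed.

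**Step 5: does another part of the plan settle which sentence governs?** The design statement in A.1, the blinded anesthesiologist in C.3(a) and C.3(g), and the pharmacy-prepared infusions all agree with the blinding sentence. They make the intent clear, but none of them says where the list is to be sent. The only instruction on delivery is the clause that names the investigators.

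**Extent.** Of the 4 roles named as blinded, 2 (surgeon and research assistant) are also named in C.2(b) as obtaining consent. This count describes which blinded roles have contact with enrollment. It does not measure bias. The documents give no block size or list length, so the number of assignments exposed cannot be counted either.

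**The case against.** The best defense is that the contradiction is conditional. It requires that the investigators include someone who is meant to be blinded, and that the list show arms. Neither is stated. The text also uses two words, list and schedule, without saying they are the same thing. A masked list, or a pharmacist counted among the investigators, would remove the conflict. Part of the front matter was not available for review, so a roster of investigators cannot be consulted. The blinding sentence is the more specific of the two and agrees with everything else in the plan, so a sensible reader would keep the surgeon and research assistant blind. On this view the clause is loose wording that needs clarifying. A further argument is that the primary outcome rests on laboratory values and written transfusion criteria, which limits what an unblinded clinician could change. Finally, a pharmacy-only remedy presumes the answer and does not say who supplies arm labels for the interim comparison in section D.

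Some of this stands. The intent to blind is plain, a drafting slip is the likely explanation, and the surgeon's inclusion is an inference. The fixing of assignments before enrollment is normal for any pre-generated sequence and is no fault in itself. The count of roles adds little.

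The rest does not remove the problem. The readings that would reconcile the sentences have no support in the text. If the list is in fact coded, the plan still has to say so. Laboratory measurement of the outcome does nothing for concealment at enrollment, and the symptomatic transfusion criterion leaves room for judgement. A slip in an instruction that staff will carry out is not harmless: the core could send the list exactly as told, and once seen it cannot be unseen. Pharmacy-only delivery follows the one exception the plan itself makes, and the core, which generates the schedule, could still supply arm labels for the interim analysis.

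**Conclusion.** The concern holds. The two sentences are inconsistent as written, and the one that governs delivery of the list is the wrong one for a concealed, double-blind trial. This must be corrected before the first patient is enrolled.

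The conclusion rests on two readings: that the investigators include the operating surgeon or others who enroll patients, which sections A.1, C.2 and C.2(b) make very likely, and that the list given to them is the usable allocation list, since nothing says otherwise. The documents do not show that anyone saw the list or that concealment failed. No magnitude of bias is claimed, because none can be derived. The sample size calculation is not affected.

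**What to change.** In section C.3(g), replace the clause on delivery of the list with wording such as: the Epidemiology & Biostatistics Core will provide the randomization list directly and only to the pharmacy before recruitment starts; investigators and all staff who recruit, treat or assess patients will have no access to it during the trial. Add one sentence stating that the core's own copy is restricted from trial staff.

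If the sponsor in fact meant a coded list, the text should say so, and should say who holds the key.

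The cost is one replaced clause and one added sentence. The core already generates the schedule and the pharmacy already prepares the infusions, so no new party, patient or visit is needed. Only the recipient of the list changes.
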